8.2.3 Analysis of Safety Endpoints

All safety summaries will be presented for the safety population. No formal statistical analysis of safety endpoints will be performed. Safety data to be evaluated includes AEs, physical examination and clinical laboratory results.

The overall observation period will be divided into three mutually exclusive segments:

1. Pre-treatment period: from day of patient's informed consent to the day before first dose of study medication.
2. On-treatment period: from day of first dose of study medication to 30 days after last dose of study medication.
3. Post-treatment period: starting at day 31 after last dose of study medication.

If dates are incomplete in a way that clear assignment to pre-, on-, post-treatment period cannot be made, then the respective data will be assigned to the on-treatment period.

8.2.3.1 Adverse Events (AEs)

Summary tables for adverse events (AEs) have to include only AEs that started or worsened during the on-treatment period, the treatment-emergent AEs. However, all safety data (including those from the pre and post-treatment periods) will be listed and those collected during the pre-treatment and post-treatment period are to be flagged.

The incidence of treatment-emergent adverse events (new or worsening from baseline) will be summarized by system organ class and or preferred term, severity (based on CTCAE grades), type of adverse event, relationship to study treatment.

Deaths reportable as SAEs and non-fatal serious adverse events will be listed by patient and tabulated by type of adverse event.

Specific safety event categories (SEC) will be considered. Such categories consist of one or more well-defined safety events which are similar in nature and for which there is a specific clinical interest in connection with the study treatment(s).

For each specified SEC, number and percentage of patients with at least one event within the SEC will be reported.

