The loss of anti-tumor immunity mediated by PD-1/PD-L1 signaling through aberrant expression of PD-L1 by the malignant cells has been well documented in solid tumors and serves as a novel and potent therapeutic target in many malignant disease types such as melanoma, lung cancer, lymphoma and others. The role of PD-1/PD-L1 pathway in myeloid derived malignancies remains poorly understood, but may offer an innovative approach at targeting the MPN hematopoietic stem cell and disrupting supporting signals from the stromal niche. Ongoing pre-clinical studies assessing the expression and function of PD-1 pathway in MPN primary cells is ongoing as a collaboration between the PI of this trial and Merck. These laboratory studies will provide insight into the role of PD-1 in escape of immune suppression of the malignant clone as well as progression and evolution of the malignant clone and the role the supporting bone marrow and splenic stroma may provide. However, it remains unclear at present if expression of PD-1 or PD-L1 by MPN cells or supporting stromal cells will predict response to pembrolizumab. Correlative studies within this trial will measure levels of expression of PD-1 and PD-L1 at baseline, after treatment with pembrolizumab at time of response assessment or at time of treatment discontinuation for any reason.

Currently, ruxolitinib is the only FDA-approved therapy for the treatment of MF and patients that have either primary or secondary resistance or intolerance to this agent have been shown to have a particularly poor outcome. No established standard of care exists for these patients. Additionally, patients with MPN-AP/BP have a dismal prognosis and there is no standard of care therapy for these patients. Outside of hematopoietic stem cell transplantation (HSCT), which is only a viable therapeutic option for a fraction of these patients, no other therapies have demonstrated clear disease course modification. Therefore, effective treatment options for these patients with advanced MPN are urgently needed. This is the subset of MPN patients that will be included in this phase II trial of pembrolizumab with a primary objective of disease response assessment after 6 cycles.

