7.2 Assessing and Recording Adverse Events

An adverse event is defined as any untoward medical occurrence in a patient or clinical investigation subject administered a pharmaceutical product and which does not necessarily have to have a causal relationship with this treatment. An adverse event can therefore be any unfavorable and unintended sign (including an abnormal laboratory finding, for example), symptom, or disease temporally associated with the use of a medicinal product or protocol-specified procedure, whether or not considered related to the medicinal product or protocol-specified procedure. Any worsening (i.e., any clinically significant adverse change in frequency and/or intensity) of a preexisting condition that is temporally associated with the use of the Merck's product, is also an adverse event.

Changes resulting from normal growth and development that do not vary significantly in frequency or severity from expected levels are not to be considered adverse events. Examples of this may include, but are not limited to, teething, typical crying in infants and children and onset of menses or menopause occurring at a physiologically appropriate time.

Merck product includes any pharmaceutical product, biological product, device, diagnostic agent or protocol-specified procedure, whether investigational (including placebo or active comparator medication) or marketed, manufactured by, licensed by, provided by or distributed by Merck for human use.

Adverse events may occur during the course of the use of Merck product in clinical trials or within the follow-up period specified by the protocol, or prescribed in clinical practice, from overdose (whether accidental or intentional), from abuse and from withdrawal.

Adverse events may also occur in screened subjects during any pre-allocation baseline period as a result of a protocol-specified intervention, including washout or discontinuation of usual therapy, diet, placebo treatment or a procedure.

Progression of the cancer under study is not considered an adverse event unless it is considered to be drug related by the investigator.

All adverse events will be recorded from the time the consent form is signed through 30 days following cessation of treatment and at each examination on the Adverse Event case report forms/worksheets. The reporting timeframe for adverse events meeting any serious criteria is described in section 7.2.3.1

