7.2.3 Immediate Reporting of Adverse Events to the Sponsor and to Merck

7.2.3.1 Serious Adverse Events

A serious adverse event is any adverse event occurring at any dose or during any use of Merck's product that:

- Results in death;
- Is life threatening;
- Results in persistent or significant disability/incapacity;
- Results in or prolongs an existing inpatient hospitalization;
- Is a congenital anomaly/birth defect;
- Is a new cancer (that is not a condition of the study);
- Is associated with an overdose;
- Is another important medical event

Refer to Table 10 for additional details regarding each of the above criteria.

Any serious adverse event, or follow up to a serious adverse event, including death due to any cause other than progression of the cancer under study that occurs to any subject from the time the consent is signed through 30 days following cessation of treatment, or the initiation of new anti-cancer therapy, whichever is earlier, whether or not related to Merck product, must be reported within 24 hours to the Sponsor and within 2 working days to Merck Global Safety.

Non-serious Events of Clinical Interest will be forwarded to Merck Global Safety and will be handled in the same manner as SAEs.

Additionally, any serious adverse event, considered by an investigator who is a qualified physician to be related to Merck product that is brought to the attention of the investigator at any time outside of the time period specified in the previous paragraph also must be reported immediately to the Sponsor and the Sponsor will report to Merck.

SAE reports and any other relevant safety information are to be forwarded to the Merck Global Safety [contact]

A copy of all 15 Day Reports and Annual Progress Reports is submitted as required by FDA, European Union (EU), Pharmaceutical and Medical Devices agency (PMDA) or other local regulators. Investigators will cross reference this submission according to local regulations to the Merck Investigational Compound Number (IND, CSA, etc.) at the time of submission. Additionally investigators will submit a copy of these reports to Merck & Co., Inc. (Attn: Worldwide Product Safety; [contact]) at the time of submission to FDA.

All subjects with serious adverse events must be followed up for outcome.

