8.1.1 Analysis Populations

8.1.1.1 Definition of Populations

Full Analysis

The Full Analysis (FA) population includes all patients who received at least one cycle of pembrolizumab and had at least one valid post-baseline efficacy assessment. The FA population will be used for all listings of raw data. Unless otherwise specified, the FA population will be the default analysis set used for all analyses.

Safety

The safety population includes all patients (primary and exploratory cohorts) who received at least one cycle of pembrolizumab and have at least one valid post-baseline safety assessment.

Per Protocol

The Per-Protocol (PP) population will consist of a subset of patients in the FA population who completed 6 treatment cycles and did not have major protocol violations or deviations. This population will be the secondary population for the analysis of the primary efficacy endpoint.

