8.1.1.2 Applicability of Population Efficacy analyses

- The primary efficacy analysis of clinical improvement (CI) or better (partial response (PR) or complete response (CR)) as shown in TABLE 5, will be based on the FA population. A secondary analysis of CI or better (PR or CR) will be performed on the PP population.
- All secondary efficacy analyses will be performed for the FA population.

Product: MK-3475
Protocol/Amendment No.:

Safety analyses

All safety analyses will be based on the safety population. In addition, specific assessments of late toxicity will be performed for patients in the safety population who are followed for safety for at least one year from treatment initiation.

Exploratory analyses

Biomarker analyses will be performed in patients for the FA population.

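### The planned death listing and table omit deaths attributed to progression, no all-cause death output is planned, and a cycle-1 death can also fall outside the safety population

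*Combined protocol and SAP*

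**What the plan says.** **Deaths.** Section 8.2.3.1 states the only death output: "Deaths reportable as SAEs and non-fatal serious adverse events will be listed by patient and tabulated by type of adverse event". Which deaths are reportable is set in section 7.2.3.1, where mandatory reporting covers serious events "including death due to any cause other than progression of the cancer under study". Section 7.2 adds: "Progression of the cancer under study is not considered an adverse event unless it is considered to be drug related by the investigator".

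**Endpoints and follow-up.** Section 4.2.4 names no survival or death endpoint for efficacy or safety. Section 8.2.3 names adverse events, physical examination and laboratory results as the safety data to be evaluated. The flow chart in section 6.1 ends 30 days after discontinuation and has no survival follow-up.

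**Populations (section 8.1.1.1).** The safety population is made up of patients "who received at least one cycle of pembrolizumab and have at least one valid post-baseline safety assessment". The Full Analysis (FA) population is "all patients who received at least one cycle of pembrolizumab and had at least one valid post-baseline efficacy assessment", and "The FA population will be used for all listings of raw data". Section 8.1.1.2 says "All safety analyses will be based on the safety population", and section 8.2.3 says the same of safety summaries. Under section 5.9, a patient who does not complete one cycle is replaced.

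**Windows.** Section 5.8 says SAEs are collected for 90 days after the end of treatment and refers to section 7.2.3.1 for this. Section 7.2.3.1 gives 30 days, or the start of new anti-cancer therapy if earlier.

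**The concern.** The trial is single arm and open label. The investigator decides whether a death was due to progression and whether that progression was drug related. Section 4.2.1 says the role of the PD-1 pathway in myeloid malignancies is poorly understood, so this judgement may be difficult. With no control arm, the count of all deaths by cohort is the one mortality figure that does not depend on it. The plan does not produce that count. A reader of the final tables would see deaths only after they had passed through the attribution, and could not tell how many had been removed. The accelerated/blast-phase (MPN-AP/BP) cohort is where this is most likely to matter, since section 4.2.1 says "patients with MPN-AP/BP have a dismal prognosis".

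**Working it through.** The plan states no mortality figure, so there is none to reproduce. The check sets the rules side by side and then shows the size under labelled assumptions.

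**Step 1: follow one death through the rules.** Take a treated patient who dies during the reporting window, with death attributed to progression and not considered drug related.
- Section 7.2: the progression is not an adverse event.
- Section 7.2.3.1: the death is not a mandatory SAE report.
- Section 8.2.3.1: it is not a death reportable as an SAE, so it is in neither the death listing nor the death table.
- Sections 4.2.4, 6.1 and 8.2.3: no survival endpoint, survival visit or all-cause death output recovers it.

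If the investigator does call the progression drug related, section 7.2 makes it an adverse event, and a fatal one is then serious and is shown.

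**Step 2: size of the omission.** Let n be the cohort size (10 for MPN-AP/BP and 24 for the chronic-phase primary cohort, MF-CP, from sections 2.1 and 4.2.3). Let d be the on-study risk of death, and s the share of deaths attributed to progression and not called drug related. Neither d nor s is in the documents; both are assumed.
- Expected deaths = n·d
- Expected deaths shown = n·d·(1 − s)
- Expected deaths omitted = n·d·s, so the relative shortfall is n·d·s / (n·d) = s
- Chance that at least one is omitted = 1 − (1 − d·s)^n

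Example: n = 10, d = 0.20, s = 0.50 gives d·s = 0.10 and 1 − 0.90^10 = 0.65.

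| Cohort | n | d | s | Deaths | Shown | Omitted | P(at least one omitted) |
|---|---|---|---|---|---|---|---|
| AP/BP | 10 | 10% | 50% | 1.0 | 0.5 | 0.5 | 0.40 |
| AP/BP | 10 | 20% | 50% | 2.0 | 1.0 | 1.0 | 0.65 |
| AP/BP | 10 | 40% | 70% | 4.0 | 1.2 | 2.8 | 0.96 |
| AP/BP | 10 | 60% | 90% | 6.0 | 0.6 | 5.4 | >0.99 |
| MF-CP | 24 | 10% | 50% | 2.4 | 1.2 | 1.2 | 0.71 |

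The relative shortfall is s whatever the cohort. The omitted deaths per patient, d·s, are more numerous in AP/BP only if d·s is higher there.

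**Step 3: cycle-1 deaths.** The safety population needs at least one cycle and one valid post-baseline safety assessment, and section 5.9 replaces patients who do not complete a cycle. A patient who is dosed on day 1 and dies before the next visit can fail either condition, whatever the cause of death. If receiving a cycle means only receiving its infusion, the first condition is met, but the assessment is still required. The plan does not say which reading applies, or whether a replaced patient stays in the safety tables.

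**Step 4: population for listings.** Section 8.1.1.1 assigns all raw-data listings to FA. Section 8.1.1.2 bases safety analyses on the safety population, and section 8.2.3.1 says all safety data are listed. For safety listings these cannot all hold. If FA governs, and 25% to 50% of SAE-reportable deaths are assumed to have no valid efficacy assessment, the 1.2 deaths shown in the third row become 1.2 × 0.75 = 0.9 to 1.2 × 0.50 = 0.6. This affects the listing only.

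**The case against.** The strongest reply is that such deaths are not lost. Section 8.2 promises that all individual case report form data will be listed, so a recorded progression death could appear there. Section 11.1 has the sponsor and the DSMB review the status of all enrolled subjects each quarter, and section 11.2 puts study status and safety information in the monitoring report. This stands as far as it goes: a reader might infer that total mortality is hidden from the DSMB, and the documents do not support that. But section 11.1 specifies no death count or cause, and a general listing is not an all-cause table.

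A reader might also infer that the FA rule removes early deaths from all safety output. It does not. The death table is a safety summary on the safety population, and the conflict concerns listings alone. Nor must a patient who dies before the post-cycle-6 assessment leave FA. The term valid is undefined, and blood counts, spleen examination and the symptom score are collected throughout treatment; if these count, many such patients enter FA. Losses would be large only if the formal assessment alone counts, which no section says.

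Finally, it is fair to say that deaths from infection, cytopenia or immune toxicity remain reportable within the window whether or not related to the drug. Only the progression attribution removes a death, and the documents give no measure of how often that attribution would be wrong.

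**Conclusion.** The concern holds in this form: followed as written, the plan yields a death listing and table that omit every death attributed to progression and not judged drug related, and nothing else in the plan reports all-cause deaths. The relative shortfall is s, the share so attributed. Over the assumed AP/BP range (d from 10% to 60%, s from 50% to 90%), the chance of omitting at least one death runs from 0.40 to above 0.99. These are illustrations, not estimates.

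Three limits apply. Understatement is not certain, since it needs at least one such death. That it would be larger in AP/BP is a plausible inference from the stated prognosis, not a documented figure. The loss of cycle-1 deaths from the safety tables is possible rather than certain, because it depends on how one cycle and a valid safety assessment are read.

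This is a cheap improvement to reporting. It does not touch the primary endpoint or the two-stage design.

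**What to change.** - **Section 8.2.3.1:** list and tabulate all deaths from first dose to the end of safety follow-up, whatever the cause, by cohort, period and attributed cause, for every patient who received any pembrolizumab. Include the all-cause count by cohort in the quarterly DSMB report.
- **Section 8.1.1.1:** define the safety population as all patients who received any dose, including those replaced under section 5.9, and name it for safety and death listings. This also removes the conflict with sections 8.1.1.2 and 8.2.3.1.
- **Sections 5.8 and 7.2.3.1:** reconcile the 90-day and 30-day SAE windows, so that the end of the death window is defined.

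Cost: one extra table and listing, a field for date and cause of death, and a vital-status check at the end of follow-up. Expedited reporting is unchanged. How long the status check must run depends on how the two windows are reconciled.

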8.2.3.2 Laboratory abnormalities

Descriptive statistics (number of observations, mean, standard deviation, minimum, median

Product: MK-3475

Protocol/Amendment No.:

and maximum values) will be presented for clinical laboratory tests (hematology, biochemistry, urinalysis), and their changes from baseline, at applicable visits.

For laboratory data, summary statistics will be presented for each parameter, together with their changes from baseline, by visit. In addition, changes from baseline will be summarized in shift tables according to severity during treatment and baseline grade. Graphical presentations of the mean value (± 2 SD) at each visit will be generated for each laboratory parameter.

8.2.3.3 Other safety data

Data from other tests (e.g., vital signs) will be listed, notable values will be flagged, and any other information collected will be listed as appropriate. Any statistical tests performed to explore the data will be used only to highlight any interesting comparisons that may warrant further consideration. Additionally, the following outputs will be produced:

Vital signs

- Shift table baseline to worst on-treatment result
- Table with descriptive statistics at baseline, one or several post-baseline time points and change from baseline to this/these post-baseline time points.

8.2.4 Analysis of Exploratory Endpoints

8.2.4.1 Biomarker: Assess expression of PD-1/PD-L1 on peripheral blood PB-MNCs, T-cells and CD34+cells by flow cytometry:

To assess expression of PD-1/PD-L1 on peripheral blood PB-MNCs, T-cells and CD34+cells, median fluorescence intensity (MFI) and the percentage of cells expressing each antigen within a gate will be estimated for each sample by flow cytometry. If there are no expression levels equal to 0 among the samples, geometric means of MFIs and percentage of cells will be reported at baseline and at the start of cycle 6. The change in geometric mean MFIs/percentage of cells from baseline to end of cycle 6 will be reported as the ratio of geometric means and tested for difference from one using a paired t-test on log transformed data. If, however, there are expression levels equal to 0, median and interquartile range of MFIs/percentage of cells will be reported at baseline and end of cycle 6 treatment. Difference between median MFIs/percentage of cells from baseline to end of cycle 6 will be tested using a Wilcoxon Signed Rank test.

8.2.4.2 Biomarker: Assess expression of PD-1/PD-L1 on bone marrow CD34+cells and supporting stromal cells by immunohistochemical staining:

To assess expression of PD-1/PD-L1 on bone marrow CD34+ cells and supporting stromal cells by immunohistochemical staining, percentages of PD-L1 and PD-1 positive tumor cells and staining intensity will be evaluated for each sample. Staining intensity will be scored

Product: MK-3475

Protocol/Amendment No.:

considering 0 as negative or trace, 1 as weak, 2 as moderate and 3 as high. A semi-quantitative approach will be used to generate an H-score for each tissue core defined as the percentage of stained cells (0–100%) multiplied by the dominant intensity pattern of staining ranging from 0 to 3. The overall semi-quantitative H-score will range from 0 to 300. If there are no H-scores of 0 among the samples, geometric means of H-scores will be reported at baseline and at the end of cycle 6 treatment. The change in geometric mean H-scores from baseline to end of cycle 6 will be reported as the ratio of geometric means and tested for difference from one using a paired t-test on log transformed data. If, however, there are H-scores of 0, median and interquartile range of H-scores will be reported at baseline and following cycle 2 treatment. Difference between median H-scores from baseline to end of cycle 6 will be tested using a Wilcoxon Signed Rank test. In addition to the semi-quantitative H-score approach, a dichotomous variable indicating expression positivity will be created. In the absence of any standardized scoring system, all cases with staining intensity ≥ 2 in more than 5% of tumor cells will be considered as positive, similarly to previous studies (Antonia *et al.*, 2013; Grosso *et al.*, 2013; Soria *et al.*, 2013). McNemar's test will be used to test for a change in the percentage of patients with positive PD-1/PD-L1 expression from baseline to the start of cycle 6 follow-up.

